7 SAFETY ASSESSMENTS

Participant safety will be monitored once an individual is enrolled in the study. The most typical negative experiences associated with tDCS include discomfort, tingling, itching, or mild burning sensations associated with the electrode application to the skin and/or electrical current, as well as headache, fatigue, or transient skin redness. During tDCS participants will be asked to report any sensations that become intolerable, so that participation can cease, and the Post-tDCS Application Survey administered after each tDCS session will include questions on the severity of any uncomfortable experiences during the procedure.

Participants might experience boredom, anxiety, or frustration during the cognitive tests. In these cases the researcher will attempt to minimize these risks by encouraging the participant and indicating that the tasks are designed to be difficult.

7.1 Specification of Safety Parameters

In over a decade of studies using tDCS, in people of different ages and psychological conditions, no significant adverse effects have been identified.

In 2011, a review of the adverse effects of tDCS (Brunoni et al., 2011, International Journal of Neuropsychopharmacology) identified 209 studies assessing a wide variety of participants, including persons from potentially vulnerable populations. Of these 209, only 74 studies reported at least one adverse effect (35%), with 43 studies explicitly reporting no adverse effects (21%) and 92 studies not reporting the presence or absence of an adverse effect (44%). Considering only the 117 studies that explicitly reported the presence or absence of an adverse effect, the most common adverse effects reported in the active stimulation groups were itching (39%), tingling (22%), headache (14.8%), burning sensation (8.7%) and discomfort (10.4%), with no reports of serious adverse effects. Importantly, similar frequencies of each of these effects were reported in the non-stimulation sham (placebo) control group (differing by 6% at most, for itching), which also requires the presence of an electrode on the skin but no sustained electrical stimulation (or only brief stimulation for the first few seconds). Overall, there were no unexpected or severe adverse events in over 40 studies with more than 600 older adults regardless of cognitive or disease status, and we are unaware of any evidence for increased risk of serious adverse effects with aging subjects. A recent meta-analysis indicates that repeated sessions of tDCS, separated by 48 hours, should pose no greater risks than those associated with a single-session (Nikolin et al., 2018). For further details on the safety of tDCS in human trials, see Bikson et al, 2016, *Brain Stimulation*.

The Actigraph device captures and records continuous mobility data related to real-world activity, mobility and sleep outcomes. There are no risks associated with the Actigraph device given it is considered completely noninvasive and comfortable. The experience on behalf of

○

○

the participant can be compared to that of a digital wristwatch. The actigraph watch captures and records continuous data related to mobility and sleep patterns. For more information on its uses and safety, refer to <https://www.actigraphcorp.com/>.

Other risks are those associated with basic computer or paper tasks, including boredom, mild fatigue, test taking anxiety, or breach of confidentiality. The expected frequency of breach of confidentiality is never.

7.2 Methods and Timing for Assessing, Recording, and Analyzing Safety Parameters

This study will only use one stimulation parameter that already is established as minimal risk, and highly tolerable for both younger and older adults. After the tDCS sessions, participants will be asked to report their sensations and rate their unease during the stimulation.

7.3 Adverse Events and Serious Adverse Events

Definitions: An **adverse event (AE)** is generally defined as any unfavorable and unintended diagnosis, symptom, sign (including an abnormal laboratory finding), syndrome or disease which either occurs during the study, having been absent at baseline, or if present at baseline, appears to worsen. Adverse events are to be recorded regardless of their relationship to the study intervention. A **serious adverse event (SAE)** is generally defined as any untoward medical occurrence that results in death, is life threatening, requires inpatient hospitalization or prolongation of existing hospitalization, results in persistent or significant disability/incapacity, or is a congenital anomaly.

During the second and third testing sessions, after the cognitive tasks, the participants will be asked to report any adverse events that have begun or worsened since the baseline session. They will also be asked explicitly describe sensations occurring during the tDCS stimulation (see Post-tDCS Application Survey in the appendix), some of which may qualify as adverse events. The Study Coordinator will record adverse events reported by participants, and the extent that they appear to be related (or unrelated) to the study procedures in the Adverse Events Survey.

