prefrontal cortex (for recent electrical models of tDCS, see Opitz, Paulus, Will et al. NeuroImage 2015) involves 3 basic steps: (1) the anodal electrode (35 cm²) is placed on the scalp over left dlPFC (F3 using the 10-20 EEG system, which typically centers over posterior middle frontal gyrus BA 8/9, Herwig et al, 2003), and the cathodal electrode is placed over the contralateral supraorbital site, thereby maximizing anodal stimulation of dlPFC and surrounding areas; (2) while sitting quietly, the brain is stimulated with mild electrical current (2 milliamperes, mA, using gradual ramping) for a total time of 20 minutes (stimulation condition), or a few seconds of mild current with no stimulation during most of 20 minutes (sham condition); and (3) post-stimulation cognitive task are administered, measuring performance enhancements (stimulation > sham). We have found this procedure reliably boosts recollection accuracy for at least 25 minutes post-stimulation, and in the literature, dlPFC effects on working memory have lasted at least 30 minutes post-stimulation (Ohn et al., 2008). Note that the cathodal tDCS electrode has been used to interfere with cognition, but the current project focuses on the anodal-based cognitive enhancement technique.

For tDCS, we will use a standard 1x1 tDCS Clinical Trials device (Soterix Medica, NY), specialized for double-blinding. Active stimulation will deliver 2 mA of current using 2

-
-

electrodes in 5 x 7 cm saline-dampened sponges. The anodal electrode is placed over areas F3 (left dlPFC) or P5 (left parietal) according to the 10-20 EEG-system, with the cathodal electrode on the contralateral supraorbital region. To balance the design for blinding, each of the 2 different electrode placements in the active stimulation conditions will be evenly represented in the sham condition (younger adults only). To rule out general arousal effects, participants are prompted to make an arousal rating immediately prior to tDCS and immediately following tDCS. (Our prior work found that tDCS did not affect arousal, compared to sham.)

Sample Size and Population

Younger adults – Frontal stimulation (n=50)

Younger adults – Parietal stimulation (n=50)

Younger adults – Sham (n=50; n=25 frontal placement, n=25 parietal placement)

Older adults – Frontal stimulation (n=50)

Older adults – Sham (n=50)

-
-

STUDY TEAM ROSTER

Principal Investigator: **[name]**

Department of Psychology
University of Chicago
*[name]

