6.2.3 Follow-up Visits (AM and PM Visits)

All participants will be enrolled in the baseline/orientation session, and they then will be assigned to active (or sham) tDCS for two follow-up experimental sessions, one in the AM and one in the PM.

- The time between each session will be at least 48 hours (i.e., at least 1 day intervening), thereby ensuring at least 1 full day of actigraphy data collected outside the lab prior to each tDCS session.
- The time between the baseline/orientation session and the final tDCS testing session should be no less than 7 days and no more than 12 days, thereby obtaining at least 7 days of actigraphy data and also providing some flexibility in the scheduling of the final session.

Follow up Assessments

Measures will include cognitive tasks, actigraphy, and the questionnaires listed in table 6.1.

-
-

Substance Use Survey See description above.

Arousal Rating *online survey* - Participants are asked about their alertness level before the encoding portion of the cognitive task adn before and after tDCS stimulation.

Post-tDCS Application Survey *online survey* - Participants report sensations during tDCS stimulation as well as what was on their mind during the stimulation.

Cognitive Tasks *computerized tasks* - See description above.

Adverse Events Questioning *verbal report* - Participants are asked if they have experience any after the baseline session. Responses are recorded in the Adverse Events Survey (see List of Administrative Logs).

6.2.4 Completion/Final Evaluation The final experimental session will be the final evaluation, and at the end of this session participants will complete a Post-Experiment Survey and finally receive a debriefing.

Post-Experiment Survey *online survey* - Participants report their sensations during the tDCS procedure, their expectations as to whether and how tDCS impacted performance, and also whether and how they believed they performed during the AM and the PM testing sessions.

Debrief Sheet *paper info sheet* - Participants are given an information sheet about the purpose of the study, which includes information about the stimulation and sham conditions (but not their own assignment), as well as hypotheses for AM and PM testing.

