The debriefing sheet also will include citations for further reading. (See Appendix). *About Early Termination:* Participants have the right to end their participation at any time. In addition, the PI may terminate participation if a participant is in obvious non-compliance with the study procedures (e.g., responding randomly or sleeping during the cognitive task) or shows signs of moderate or severe adverse events associated with the study procedures (e.g., excessive discomfort with the tDCS electrodes).

-
-

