7.5 Follow-up for Adverse Events

Any unresolved AE that is possibly related to the study procedures will result in halting the subject's participation in the study. The study is minimal risk and no long-lasting adverse events are expected. Any AE that renders the participant ineligible to be in the study (as per the inclusion/exclusion criteria) will also be resolved by halting participation in the study.

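### The only scheduled adverse-event question follows each stimulation, so the section 7.5 halt can act in time on a between-visit event only if someone volunteers or notices it

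*Protocol*

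**What the plan says.** Protocol section 7.3 fixes when AEs are asked about: "During the second and third testing sessions, after the cognitive tasks, the participants will be asked to report any adverse events". The question looks back to the baseline session, so events between visits are meant to be captured. Section 6.2.3 describes the same question ("Participants are asked if they have experience any after the baseline session") and does not place it earlier in the visit. Table 6.1 marks AE questioning at the AM and PM visits only, and marks the safety inclusion/exclusion survey in the screening column only.

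Section 7.5 sets two mandatory halts. The first reads "Any unresolved AE that is possibly related to the study procedures will result in halting" the subject's participation. The second, for "Any AE that renders the participant ineligible to be in the study", has the same result.

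Two other routes can stop a session. Under section 7, participants are asked during tDCS to report sensations they cannot tolerate. Under the early-termination paragraph of section 6.2.4, the PI may end participation if someone "shows signs of moderate or severe adverse events associated with the study procedures".

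**The concern.** A mandatory halting rule needs a check that comes before the exposure it is meant to prevent. Here the one scheduled check comes after it. Suppose a headache starts the evening after the first tDCS visit and is still present at the second. Section 7.5 says participation halts, but staff are not told to ask until the second stimulation is over. The same applies to a new exclusion arising between visits, such as a head injury needing hospitalization or a new psychoactive medication.

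What is at stake is an avoidable 20-minute active or sham session in someone whom the protocol says should be halted. No estimate or test of efficacy is affected.

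**Working it through.** The documents give no figure to reproduce. The check is one of sequence, plus simple arithmetic on visit spacing.

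**1. Order within a tDCS visit.** The standard anodal procedure (Protocol, Interventions and Duration) runs as electrode placement, 20 minutes of current, then post-stimulation cognitive tasks. Section 6.2 puts the working memory task after the episodic task. Encoding for the episodic task comes earlier in the visit, but the tasks as a whole end after stimulation. A question placed after the tasks is therefore a question after stimulation.

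**2. Other questions at these visits.** Before stimulation the protocol describes an arousal rating ("participants are prompted to make an arousal rating immediately prior to tDCS and immediately following tDCS"). Table 6.1 also lists a substance use survey and a sleep diary at each visit. As described, these cover alertness; caffeine, nicotine and alcohol; and sleep. None is described as asking about AEs or the section 4.2 exclusions. The Post-tDCS Application Survey concerns the stimulation just given. Eligibility screening is done within 3 months before participation (section 6.2.1), with no repeat described. AE prompts described before stimulation: 0 at the 2 tDCS visits.

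**3. Length of the unprompted intervals.** Inputs from section 6.2.3: "The time between each session will be at least 48 hours", and the time from baseline to the final tDCS session "should be no less than 7 days and no more than 12 days". Let g1 be the days from baseline to the first tDCS visit, and g2 the days from the first to the second.

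- Constraints: g1 ≥ 2, g2 ≥ 2, 7 ≤ g1 + g2 ≤ 12.
- Longest single gap: 12 − 2 = 10 days, so each gap is 2 to 10 days.
- On the 7-day schedule: 7 − 2 = 5, so each gap is 2 to 5 days.
- Both gaps together: 7 to 12 days per participant.

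**4. Number of gaps.** Planned arms (Sample Size and Population): younger adults 50 frontal, 50 parietal, 50 sham; older adults 50 frontal, 50 sham.

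- Participants: 50 × 5 = 250.
- Gaps: 250 × 2 = 500.
- Gaps between the two tDCS visits: 250, of which active 50 + 50 + 50 = 150 and sham 50 + 50 = 100.

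**5. What the late question can still do.**

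| AE starts | First scheduled prompt | Stimulation that prompt can still prevent |
|---|---|---|
| Between baseline and first tDCS visit | After first stimulation | Second only |
| During first tDCS visit, reported and unresolved that day | End of that visit | Second |
| Between first and second tDCS visits | After second stimulation | None |

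The middle row works as intended and is outside this point.

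**The case against.** The strongest case is about weight.

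- **The first gap has little to catch.** Before the first tDCS visit no current has been given, so an AE possibly related to study procedures is unlikely. This is fair for the first halting rule. The ineligibility rule still applies in both gaps, so 500 is a correct count of exposure to the question order. The 250 gaps between tDCS visits are the ones where both rules matter.
- **The remaining case is narrow.** Effects at the first tDCS visit are asked about that day. What is left must start later, persist to the next visit, and be neither volunteered nor noticed. The protocol describes tDCS effects as mild and short-lived, and cites evidence that sessions 48 hours apart add no risk. This stands, and it is why the point is minor.
- **Section 7.5 may not be an arrival check.** Its heading concerns follow-up, and it says what happens once an AE is known. That is true, but a mandatory halt serves little purpose if the scheduled question that should trigger it comes after the last stimulation.
- **The appendix forms were not available.** One of them could contain an AE question on arrival. Nothing in the body text says so, and section 7.3 places the question explicitly. The conclusion is limited to what the protocol body describes.
- **Re-checking exclusions goes beyond AEs.** Section 7.5's second rule turns on eligibility, so a short check of changes in section 4.2 items serves that rule.

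**Conclusion.** The concern holds. Followed as written, the protocol first asks about a between-visit AE after the next stimulation, and for an event arising between the two tDCS visits that is the last one. In those intervals the section 7.5 halts depend on the participant volunteering the event or on staff noticing it.

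The order applies to 500 gaps of 2 to 10 days each, 250 of them between tDCS visits. These figures assume full enrolment of 250 and visits kept within the stated windows. They do not measure harm: no rate of between-visit AEs is given and none is assumed. The conclusion also assumes that the unseen appendix forms contain no AE question on arrival.

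This is a cheap improvement to participant safety in a minimal-risk study. Sample size, error rates and the planned analyses are untouched.

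**What to change.** Amend section 7.3 and the AM and PM columns of table 6.1. On arrival at each tDCS visit, before electrodes are placed, ask about AEs since the previous visit and about any change in the section 4.2 exclusions. Keep the end-of-visit question for events since that day's stimulation. Record both in the existing Adverse Events Survey. Section 7.5 can stay as it is. The arousal rating already provides a contact point just before stimulation.

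The between-visit time not asked about before the next stimulation then falls from 7 to 12 days per participant to 0.

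The cost is a minute or two per visit and one wording amendment. Some visits may be rescheduled or halted on arrival. Section 8 already replaces participants who do not complete both tDCS sessions, so each such halt costs one replacement. All arms get the same question, so blinding is not affected.

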7.4 Reporting Procedures

All adverse experiences will be recorded in the Adverse Events Survey . If the event is classified as a Serious Adverse Event, the PI will be notified immediately. The PI will then notify the NIA, the DSMB chair, as well as the IRB within 24 hours, at which time they may ask for additional information.

-
-

AEs or SAEs that may occur during the study (regardless of their relationship to the study procedures) will be submitted in routine reports to the DSMB, prior to DSMB conference calls.

7.5 Follow-up for Adverse Events

Any unresolved AE that is possibly related to the study procedures will result in halting the subject's participation in the study. The study is minimal risk and no long-lasting adverse events are expected. Any AE that renders the participant ineligible to be in the study (as per the inclusion/exclusion criteria) will also be resolved by halting participation in the study.

7.6 Safety Monitoring

An NIA-appointed Data and Safety Monitoring Board will review the project, and adherence to the Data Safety and Monitoring Plan.

8 INTERVENTION DISCONTINUATION

Participants may withdraw voluntarily from participation in the study at any time and for any reason. Because the adverse events associated with tDCS are mild and transient, we will not continue to follow participants that withdraw from the study. Participants reporting headache will be given the option to rest in the lab until the situation resolves.

Data from participants that discontinue without completing both experimental testing sessions will be replaced with a new participant assigned to the same condition.

In the event that participation in the study is halted during or following tDCS, the participant will be asked to complete the Post-tDCS Application Survey and also will receive debriefing.

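### No contact is planned to learn the outcome of an adverse event that is unresolved and possibly related when a participant leaves the study

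*Protocol*

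**What the plan says.** Four parts of the Protocol bear on this; the SAP text available does not address it.

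- **Section 7.5 (Follow-up for Adverse Events):** "Any unresolved AE that is possibly related to the study procedures will result in halting" the person's participation. The section adds that nothing long-lasting is expected. It names no later contact and no recording of outcome.
- **Section 8 (Intervention Discontinuation):** "Because the adverse events associated with tDCS are mild and transient, we will not continue to follow participants that withdraw from the study". The next sentence lets participants with headache rest in the lab until it passes. If participation is halted during or after tDCS, "the participant will be asked to complete the Post-tDCS Application Survey and also will receive debriefing".
- **Section 6.2.4 (Completion/Final Evaluation):** "The final experimental session will be the final evaluation". The early-termination paragraph that follows lets the investigator stop a participant who "shows signs of moderate or severe adverse events associated with the study procedures".
- **Sections 6.1, 7.3 and 7.4:** AE questioning is scheduled at the AM and PM visits. Section 7.3 places it in each of them: "after the cognitive tasks, the participants will be asked to report any adverse events that have begun or worsened since the baseline session". AEs are logged with a judgement of relatedness and go to the DSMB in routine reports. A serious event goes to the NIA, the DSMB chair and the IRB within 24 hours, "at which time they may ask for additional information".

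**The concern.** Halting ends exposure, but it does not show whether the event ended. A section headed as follow-up gives no way of finding out. The reason offered, that tDCS effects are mild and brief, describes the typical event. An AE classed as unresolved has already departed from that pattern, as has one classed as moderate or severe, and the protocol foresees both.

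At stake are participant care and the completeness of the AE record. If an open event worsened or needed treatment after the person left, the study would hear of it only from that person. The 24-hour route for serious events and the safety review in section 9.3 can work only on what the study comes to know. No efficacy estimate, sample size or error rate depends on this.

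**Working it through.** The plan states no figure to reproduce. The check sets the sections side by side and then sizes the fix.

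**1. Ways of leaving with an open, possibly related AE**

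- *Voluntary withdrawal:* section 8 says outright that there is no further follow-up.
- *Halted by the study:* section 7.5 ends participation and is silent on later contact. Section 8 adds the Post-tDCS Application Survey and debriefing if the halt comes during or after tDCS.
- *Completion:* section 6.2.4 makes the last tDCS visit the final evaluation. Nothing is left to halt, so section 7.5 provides no action.

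None of the three leads to a contact at which the outcome would be learned. For withdrawal this is an explicit rule. For the other two it follows from the silence of section 7.5 and the absence of any later visit or call.

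**2. Whether the stated rationale reaches these cases**

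Section 7.1 gives types and frequencies of effects, reports no serious ones, and says repeated sessions 48 hours apart "should pose no greater risks than those associated with a single-session". It gives no durations. In the review it cites, 74 + 43 = 117 of 209 studies (56%) stated whether an AE occurred, and 92 (44%) did not. Those counts bear on how often effects are reported, not on how long they last. The section supports the absence of a later survey of everyone. It does not address an event already seen to persist.

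**3. Timing of a halt**

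- Section 6.2.3 requires at least 48 hours between sessions and at most 12 days from baseline to the last session.
- The two tDCS visits are therefore 2 to 12 − 2 = 10 days apart.
- If a halt takes effect at the first tDCS visit, it cancels the second, which is the only later AE questioning.
- If the event is judged unresolved only at the second visit, it has been rechecked once, and what remains is the gap after that visit.
- Section 7.5 does not say when the judgement is made, so both readings are open.

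**4. Counts**

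- Participants: 150 younger + 100 older = 250.
- Planned AE questionings: 250 × 2 = 500, of which 250 are at the final visit.
- Share leaving with an open, possibly related AE: not given. Assume 1%, 2% or 5%: 0.01 × 250 = 2.5; 0.02 × 250 = 5; 0.05 × 250 = 12.5 participants.
- Two contacts each (assumed): 5, 10 or 25 contacts.
- Ten minutes per contact (assumed): 50, 100 or 250 minutes, that is 0.8, 1.7 or 4.2 hours over the whole study.

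**5. Early stopping**

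Section 7.3 places the AE question after the cognitive tasks. As written, someone who stops after tDCS but before the end of those tasks does not reach it. Section 8 replaces leavers, so with a stopping share d the number of leavers is 250/(1 − d) − 250. This gives 5.1 for an assumed d of 2%, 13.2 for 5% and 27.8 for 10%. These are upper limits, because some will stop before any tDCS or after the question has been asked.

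**The case against.** The strongest reply is that this is a reasoned choice in a minimal-risk study. The rationale appears in sections 7.1, 7.5 and 8. Section 7.1 reports no severe or unexpected events across more than 40 studies that included upwards of 600 older people. An NIA-appointed DSMB reviews the protocol. AEs are recorded and reported, severe ones can trigger a safety review under section 9.3, and the bodies told of a serious event may ask for more. All of this stands, and it is why the point is minor. None of it is a contact with the participant to learn an outcome.

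A reader might infer four stronger claims that the documents do not support.

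- *Halting is the only response.* It is not: headache has the in-lab rest option, and the event is logged and reported.
- *The no-follow-up sentence in section 8 covers everyone who leaves.* It concerns those who withdraw. For halted participants and completers the gap rests on section 7.5 and the lack of later contact.
- *A participant with an open AE at the first tDCS visit is never asked again.* That holds only if the halt takes effect at that visit.
- *Early stoppers have no AE capture.* Section 6.1 schedules AE questioning at both tDCS visits. The Post-tDCS Application Survey records sensations that may count as AEs, and an AE that causes the stop is already known. What remains is an unmentioned event, not a stimulation sensation, in someone who stops for another reason before the tasks end.

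It can also be said that a claim of absence is hard to establish from this material. The consent and contact pages were removed, and neither the separate Data Safety and Monitoring Plan nor the content of the AE survey form is shown. Any of them might deal with outcome. That lowers confidence to moderate.

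**Conclusion.** The point holds as a minor one. In the visible protocol no contact is provided to learn the outcome of an AE that is unresolved and possibly related when a participant withdraws, is halted or completes. The mild-and-brief rationale justifies not surveying everyone, but does not extend to an event already known to be open.

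The size is small. On the assumed 1% to 5%, about 3 to 13 of 250 participants would be concerned. Those rates, like the stopping shares, serve to price the remedy; they are not evidence of harm, and the gap in the text does not depend on them. Nothing here suggests that the stimulation is unsafe or that same-day events go unsolicited. Efficacy results are untouched. The conclusion assumes that the documents not shown contain no follow-up rule.

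**What to change.** 1. In sections 7.5 and 8, state that any AE that is unresolved and possibly related when a participant withdraws, is halted or finishes the final visit will be followed by phone or with the existing AE survey until it resolves or contact ends, if the participant agrees.
2. In section 8, limit the no-follow-up rule for withdrawals to outcome data.
3. As a small clarification in section 8, ask the existing AE question at the point of stopping for anyone who leaves after tDCS but before the end of the cognitive tasks, alongside the Post-tDCS Application Survey.

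No later survey of all completers is requested.

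The cost is two or three sentences, matching consent wording, and about 1 to 4 hours of coordinator time under the assumed rates. Item 3 adds one question for at most about 5 to 28 people if 2% to 10% stop. Some leavers will decline or not reply. Answers given later will follow a debriefing that explains the sham condition, although participants are not told their own assignment. Visits, blinding and sample size do not change.
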